5 SIGNIFICANCE LEVELS AND HANDLING OF TYPE I ERROR

5.1 Interim Analysis

Eight interim analyses were planned to check for safety with regard to combined outcome and mortality and re-hospitalization. The significance was corrected for multiple testing using the one-sided 5% limit of Pocock in the direction of harm from the experimental management program.

These analyses do not materially affect the type I error rate for the final analysis of efficacy that will examine whether the experimental management program reduces risk in relation to the control group (see Section 5.2).

5.2 Final Analysis

The overall experiment-wise significance level for this study is at a two-tailed 5% level.

6 DATA ANALYSIS SETS AND BASELINE AND FOLLOW-UP VARIABLES

All analyses will be conducted on the Intention to Treat (ITT) dataset according to the treatment group allocated by randomization. This means that all subjects will be kept in their assigned treatment groups, even those who were intended to be in the active group, but for some reason did not receive the experimental disease management program and vice versa.

7 EFFICACY ANALYSIS

7.1 Primary analysis of primary endpoint

The analyses to be conducted at the final statistical analysis are described in this Section. The primary endpoint is time to the combined outcome (mortality or hospitalization due to heart failure, whichever happens first). The Cox regression model will be used to compare the treatment groups with respect to this outcome, and the comparison will be adjusted for the following baseline factors: sex, age (5 categories: <50, 50-59, 60-69, 70-79, 80+), center, and functional impairment (NYHA class) at baseline.

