Comparison between the two interventions (i.e. Disease Management, the study intervention, and Usual Care, the control intervention) will be made by log-rank test, where an event is defined as hospital admission due to heart failure or death from any cause. In this analysis, the occurrence of any of these two events is defined as 'failure', and the time until the first event (hospital admission or death) will be defined as the time-to-failure. The analysis will be according to intention-to-treat, meaning that patients' data will be analysed according to their assigned intervention. The log-rank test will be one-sided at a significance level of 2.5%, where the alternative hypothesis is that this time will be longer in the study intervention group. Since the Data Monitoring Committee acts as a safety committee and the tests used for this purpose will be in the other direction, looking for poorer results in the study intervention group, no correction for multiple comparisons are needed.

Secondary analyses

There will be several secondary analyses to support the primary hypothesis. They will include:

- (i) Comparisons of baseline factors among the two study groups, e.g. age, NYHA functional classification, 6-min. walk test, left ventricular ejection fraction, type of heart failure, plasma creatinine and heart failure center;
- (ii) Adjustment for these baseline factors will be made using the Cox proportional hazards model;
- (iii) An interaction between the NYHA functional classification and study group will be tested;
- (iv) An interaction between the time of recruitment and study group will be tested, since we expect a 'learning effect' in operating the study intervention;

In addition, the two study groups will be compared for the other secondary outcomes, for example:

- (i) The number of hospital admissions for heart failure per year;
- (ii) Death from all causes;
- (iii) NYHA classification tested every 6 months during follow-up;
- (iv) Health related quality of life and depression symptoms tested every 6 months during follow-up;

Total costs will be compared between the two interventions.

The statistical methods for these comparisons will be chosen according to the distribution of each outcome (categorical, ordered or continuous). Each outcome will be tested in univariate and multiple variable models.

Potential bias and ways to reduce its effect

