1.5 Randomization

Conducted within 10-patients' blocks and stratified by heart failure center, with 1:1 ratio between the two study arms, maintaining allocation concealment.

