1.11 Study Dates

First patient recruited: August, 2007

Last patient recruited: June, 2011

Total number of patients randomized: 1,361 (one not included in the analysis because informed consent was not provided (protocol violation))

Minimum duration of follow-up: 1 year

Maximal follow-up period: 5 years.

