7.2 Secondary analyses

7.2.1 Secondary Analyses of the Primary Endpoint

All analyses will be adjusted for the same baseline factors as mentioned in 7.1 plus others that are unbalanced between the treatment groups, i.e are significantly different at the 10% significance level when entered separately. The additional baseline factors that will be considered are:

- A. 6-minute walk test
 - B. Recruited after hospitalization or from the community
 - C. Year of recruitment
 - D. Underlying cause of heart failure: ischemic/non-ischemic
 - E. Type of heart failure (left ventricular ejection fraction (LVEF) %): preserved (LVEF (%) \geq 50%)/ non-preserved (LVEF%)<50%.
 - F. Co-morbidity: diabetic/ non-diabetic
 - G. Adherence to HF medication
1. The principal statistical analysis mentioned in 7.1 with additional adjustment.
 2. Cox regression for the outcome mortality from any cause.
 3. Cox regression with the outcome re-hospitalization due to heart failure.

For each of these outcome models, the following interactions will be tested:

- i. Between arm and year of recruitment
- ii. Between arm and center
- iii. Between arm and recruitment after hospitalization or from the community
- iv. Between arm and underlying cause of HF (ischemic/ non-ischemic)
- v. Between arm and type of HF (preserved (LVEF \geq 50%)/ non-preserved (LVEF<50%))
- vi. Between arm and co-morbidity (diabetic/ non-diabetic)
- vii. For outcomes (1)-(3) above, we will investigate the interaction between treatment arm and time from entry to the trial. This is equivalent to testing the assumption

that the hazards in the two treatment arms are proportional over time – what is known as the proportional hazard assumption.

7.2.2 Analyses of Secondary Endpoints (events are counted until 31/7/12, ignoring early termination)

Fourteen secondary end-points will be analyzed to provide insight into the benefits of the disease management program. The analyses will be conducted on the ITT dataset. All the analyses will be adjusted for the following baseline factors:

- A. Sex
- B. Age (in five groups, as above)
- C. Center
- D. Functional impairment (NYHA) at baseline

- 1. Cox regression with mortality due to any cause.
- 2. Cox regression with re- hospitalization due to HF
- 3. Regression with total days of hospitalization and total number of hospital admissions due to HF
- 4. Regression with total days of hospitalization and total number of hospital admissions due to acute exacerbation

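### The primary Cox model in SAP 7.1 leaves out baseline creatinine, LVEF and recruitment track; prespecifying them would gain some power, by an amount that depends on assumptions

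*Supplement*

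**What the plan says.** For the primary endpoint, SAP 7.1 specifies a Cox model adjusted for sex, age in five bands, "center, and functional impairment (NYHA class) at baseline". No other covariate enters the primary comparison.

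The three factors at issue are all on the baseline form (protocol Appendix C): creatinine among the blood tests, LVEF in the echocardiography table, and type of referral in the referral section.

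The protocol's statistical section, under secondary analyses, lists baseline factors that include "left ventricular ejection fraction, type of heart failure, plasma creatinine and heart failure center" and says a Cox model will adjust for them. The protocol's main analysis is an unadjusted log-rank test.

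SAP 7.2.1 lists further candidates for a secondary analysis of the primary endpoint. They include "Recruited after hospitalization or from the community" and LVEF split at 50%. Each is added only if the arms differ on it at the 10% level. Creatinine is not on the list. The same section tests arm-by-track and arm-by-LVEF-type interactions.

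**The concern.** In a Cox model, leaving out a factor that predicts the outcome pulls the arm hazard ratio towards 1 and lowers power, even when the factor is perfectly balanced between arms. Baseline values that are already collected can recover this without new patients or measurements.

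The secondary route does not do the job. A test of baseline imbalance says nothing about prognostic value, so a strong predictor that happens to be balanced would never be used. Creatinine cannot enter under any rule in the SAP, although the protocol thought it worth adjusting for. Recruitment track separates patients admitted under different eligibility rules. NYHA class reflects that only in part: a class III patient just discharged and a class III community patient look alike to the primary model.

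What is at stake is the power of the single primary test.

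**Working it through.** **1. Reproduce the plan's own power figure.** The protocol's sample size section assumes 33% of usual-care patients re-hospitalized for heart disease at 12 months, an odds ratio (OR) of 0.67 or 0.58, 600 per arm and a two-sided 5% test.
- OR 0.67: odds 0.33/0.67 × 0.67 = 0.33; risk 0.33/1.33 = 24.8%. The two-proportion test gives 88.0% power (stated: 89%).
- OR 0.58: risk 22.2%; power 98.7% (stated: 99%).

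Both figures are reproduced closely.

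**2. Put the planned effect on the hazard scale**, assuming constant hazards: HR = ln(1 − treated risk)/ln(1 − control risk).
- OR 0.67: ln(0.752)/ln(0.67) = 0.71.
- OR 0.58: ln(0.778)/ln(0.67) = 0.63.
- Cross-check at HR 0.71: expected events 600 × (0.330 + 0.248) = 347, and the Schoenfeld formula gives 88.5%.

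**3. Allow for the composite.** The protocol has no power calculation for the composite endpoint and expects results similar to re-hospitalization. It separately assumes 18% control mortality with OR 0.80, which gives 14.9% on treatment. Treating death and re-hospitalization as independent (an assumption):
- control risk 1 − 0.82 × 0.67 = 45%;
- treated risk with OR 0.67: 1 − 0.851 × 0.752 = 36%, so HR about 0.75;
- with OR 0.58 for re-hospitalization, HR about 0.69.

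An effect somewhat weaker than 0.71 is therefore compatible with the plan's own inputs.

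**4. Simulate the primary model with and without the omitted score.**
- From the SAP: 1,360 analysed patients ("Total number of patients randomized: 1,361", less one without consent), allocation "with 1:1 ratio between the two study arms, maintaining allocation concealment", follow-up of 1 to 5 years ("Minimum duration of follow-up: 1 year") and a two-sided 5% test ("The overall experiment-wise significance level for this study is at a two-tailed 5% level").
- From the protocol: 33% control risk at 12 months, which is the re-hospitalization figure, because none is given for the composite.
- Assumed, with no figure in the documents: exponential hazards, follow-up uniform over 1 to 5 years, no dropout, log-hazard SD 0.4 for the four existing covariates, and SD 0.3, 0.5 or 0.7 for what creatinine, LVEF and track add beyond them. These last values mean a hazard ratio per SD of exp(0.3) = 1.35, exp(0.5) = 1.65 and exp(0.7) = 2.01.
- Each scenario had 1,200 to 2,500 runs, with Monte Carlo error of roughly 1 point. Gains are taken from unrounded powers.

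| Conditional HR | SD 0.3: power without → with (gain) | SD 0.5 | SD 0.7 |
|---|---|---|---|
| 0.63 | 100 → 100 (0.0) | 100 → 100 (0.0) | 99.8 → 100 (0.2) |
| 0.71 | 99.7 → 99.8 (0.1) | 99.0 → 99.8 (0.8) | 97.2 → 99.6 (2.3) |
| 0.75 | 96.9 → 98.0 (1.1) | 96.0 → 98.5 (2.5) | 91.7 → 98.3 (6.6) |
| 0.80 | 86.8 → 89.5 (2.7) | 79.9 → 86.9 (7.0) | 74.3 → 87.3 (13.1) |

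With a weak omitted score (SD 0.1 or 0.2) at HR 0.80, the gain is 0.8 or 1.0 points.

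The gain at the planned effect is small because power there is already 97% or more. Event fractions at HR 0.71 were 0.556 to 0.591 across the SDs tried, or about 756 to 804 events in 1,360 patients, against 347 in the protocol's 12-month calculation. With only 1,200 patients and 12 months of follow-up, the gains at HR 0.71 are 1.2, 2.6 and 6.0 points.

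**5. Effect on the estimate.** At conditional HR 0.71 and SD 0.5, the average estimate is 0.734 without the omitted score and 0.711 with it. At HR 0.80 the estimates without it are 0.806, 0.818 and 0.830 for the three SDs.

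**The case against.** The strongest defence is that nothing in SAP 7.1 is wrong. The model is prespecified, contains the stratification factor, two demographic factors and a severity measure, and was finalised before data analysis. At the planned effect it has ample power. This all stands.

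Three further objections stand in part.
- NYHA carries some of the track information, since under the current criteria class II patients enter only after a hospital admission. It does not separate the tracks within classes III and IV, nor for community patients who entered before the February 2008 amendment on criteria not tied to classes III and IV.
- The interaction models in SAP 7.2.1 would normally include main effects of track and LVEF type. They are secondary, however, and do not put those factors into the primary test.
- A four-covariate model avoids relying on imputed laboratory or echocardiography values. The documents give no baseline missingness, so the size of that advantage is unknown.

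A reader might infer that the SAP went back on a promise in the protocol. It did not: the protocol named creatinine and LVEF for secondary adjustment only, beside an unadjusted primary test, and a change of plan is no fault in itself. A reader might also take the shift from 0.711 to 0.734 as bias. It reflects non-collapsibility of the hazard ratio: the two models estimate effects conditional on different covariate sets.

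**Conclusion.** The point holds as an efficiency improvement. Three plausible prognostic factors that the trial already collects are outside the primary model, one of them is outside the SAP altogether, and the 10% imbalance rule is not a sound way to bring in the other two.

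For an omitted-score SD of 0.3 to 0.7, the gain is about 0 to 2 points of power at the planned effect (HR about 0.63 to 0.71), about 1 to 7 points at HR 0.75 and about 3 to 13 points at HR 0.80. At HR 0.80 it is about 1 point if the SD is only 0.1 to 0.2.

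It is tempting to state one fixed loss, such as 3 to 8 points. The documents do not support that: they give no prognostic strength for any covariate, and a loss of that size at the trial's full size and follow-up generally needs an effect weaker than the planned one. The range rests on assumed SDs, constant hazards, no dropout and a control risk borrowed from re-hospitalization.

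**What to change.** In SAP 7.1, add to sex, age, centre and NYHA, before any comparison by arm and whatever the baseline balance:
- baseline creatinine, for example on the log scale;
- LVEF as a continuous variable, in a functional form fixed in advance, since the trial includes both preserved and reduced LVEF;
- recruitment track, after hospital admission or community.

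State that missing baseline values are handled by the multiple imputation of SAP section 2, and that the reported hazard ratio is conditional on the enlarged covariate set. Report the four-covariate model as a sensitivity analysis.

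The cost is a change of wording and a few more parameters in a model with several hundred events. No new data are needed, and the type I error is unchanged. The small downside is that the primary model then relies on some imputed baseline values.

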7.2 Secondary analyses

7.2.1 Secondary Analyses of the Primary Endpoint

All analyses will be adjusted for the same baseline factors as mentioned in 7.1 plus others that are unbalanced between the treatment groups, i.e are significantly different at the 10% significance level when entered separately. The additional baseline factors that will be considered are:

- A. 6-minute walk test
 - B. Recruited after hospitalization or from the community
 - C. Year of recruitment
 - D. Underlying cause of heart failure: ischemic/non-ischemic
 - E. Type of heart failure (left ventricular ejection fraction (LVEF) %): preserved (LVEF (%) \geq 50%)/ non-preserved (LVEF%)<50%.
 - F. Co-morbidity: diabetic/ non-diabetic
 - G. Adherence to HF medication
1. The principal statistical analysis mentioned in 7.1 with additional adjustment.
 2. Cox regression for the outcome mortality from any cause.
 3. Cox regression with the outcome re-hospitalization due to heart failure.

For each of these outcome models, the following interactions will be tested:

- i. Between arm and year of recruitment
- ii. Between arm and center
- iii. Between arm and recruitment after hospitalization or from the community
- iv. Between arm and underlying cause of HF (ischemic/ non-ischemic)
- v. Between arm and type of HF (preserved (LVEF \geq 50%)/ non-preserved (LVEF<50%))
- vi. Between arm and co-morbidity (diabetic/ non-diabetic)
- vii. For outcomes (1)-(3) above, we will investigate the interaction between treatment arm and time from entry to the trial. This is equivalent to testing the assumption

that the hazards in the two treatment arms are proportional over time – what is known as the proportional hazard assumption.

7.2.2 Analyses of Secondary Endpoints (events are counted until 31/7/12, ignoring early termination)

Fourteen secondary end-points will be analyzed to provide insight into the benefits of the disease management program. The analyses will be conducted on the ITT dataset. All the analyses will be adjusted for the following baseline factors:

- A. Sex
- B. Age (in five groups, as above)
- C. Center
- D. Functional impairment (NYHA) at baseline

- 1. Cox regression with mortality due to any cause.
- 2. Cox regression with re- hospitalization due to HF
- 3. Regression with total days of hospitalization and total number of hospital admissions due to HF
- 4. Regression with total days of hospitalization and total number of hospital admissions due to acute exacerbation
- 5. Regression with total days of hospitalization and total number of hospital admissions due to HF complications (including HF treatment adverse effects)
- 6. Regression with total days of hospitalization and number of hospital admissions for any cause
- 7. Functional impairment (NYHA class) at 6 month intervals
- 8. 6-minute walk test at 6 month intervals (in whole meters including zeros, probably will be categorized).

The 8th and 9th secondary endpoints are ordered outcomes. Therefore the proportional odds model using the GEE method implemented in the Genmod procedure (SAS 9.2), with repeated measurements, will be fitted. The proportional odds assumption will be tested and if violated a partial proportional odds model will be fitted.

- 9. Quality of life
SF36 at 6 month intervals – (score in 2 major domains (physical, mental)) – the GEE method implemented in the Genmod procedure (SAS 9.2), with repeated statement, will be fitted. If the data appear continuous then we will use GEE for a continuous outcome; if there are clumps of measurements (at 0 or 100 say), then we will categorize the data and use the proportional odds model version of GEE.
- 10. Regression model with repeated measures for Depression (PhQ9) at 6 month intervals adjusted for baseline value (subgroup with baseline value)
- 11. Regression model with repeated measures for BNP since 2009 at 6 month intervals, adjusted for baseline value (subgroup with baseline value).
- 12. Adherence to guidelines for recommended medical treatment. Two types of medical treatments will be considered: ACE-I/ARB's and Beta-blockers. We will examine adherence to each individual type and to their combination. Adherence to their combination will be scored 0,1 or 2 for patients who do not take any of the two types, patients taking only one type and patients taking both types of medicine, respectively. The two arms will be compared at 6 month intervals for their adherence to medical treatment using the proportional odds model or the partial proportional odds model using the Genmod procedure (SAS 9.2) with repeated statement.

Statistical Analysis Plan

13. A separate analysis will be conducted on the total cost for health care provider to all health care services supplied to the disease management program (not including cost of disease management manpower and infrastructure designated for the study disease program).
14. Regression model with repeated measures for total cost of disease management at 6 month intervals.

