1.3 Eligibility

- Adult men and women (age: >18 years) with HF who are ensured by Maccabi Health Services in Israel, recruited either <2 months after hospital admission for acute presentation of the disease, or from the community
- Disease severity, assessed by New York Heart Association (NYHA) functional stage:
 - II-IV for patients recruited after hospital admission
 - III-IV for patients recruited from the community
- Heart failure diagnosed according to European Society of Cardiology (ESC) guidelines

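### SAP 7.2.1 picks its additional covariates by a 10% between-arm imbalance test, so these secondary Cox models are adjusted by chance and not by prognosis

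*Supplement*

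**What the plan says.** The primary Cox model in SAP 7.1 has a fixed list of covariates: "sex, age (5 categories: <50, 50-59, 60-69, 70-79, 80+), center, and functional impairment (NYHA class) at baseline". SAP 7.2.2 uses the same four factors for the secondary endpoints. Neither section contains a data-driven selection step.

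SAP 7.2.1 covers three Cox analyses: the 7.1 analysis with further adjustment, all-cause mortality, and re-hospitalisation for heart failure. Each uses the four fixed factors "plus others that are unbalanced between the treatment groups, i.e are significantly different at the 10% significance level when entered separately". The sentence "The additional baseline factors that will be considered are" introduces seven candidates:

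- A: 6-minute walk test
- B: recruitment track ("Recruited after hospitalization or from the community")
- C: year of recruitment
- D: ischaemic or non-ischaemic cause
- E: preserved or non-preserved LVEF
- F: diabetes
- G: adherence to heart failure medication

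The same section plans interaction tests of arm with several of these, including "Between arm and recruitment after hospitalization or from the community".

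SAP 1.5 describes allocation in blocks of 10, "stratified by heart failure center, with 1:1 ratio between the two study arms", with concealment. The protocol's own secondary analysis plan has no imbalance test: after naming examples of baseline factors it says "Adjustment for these baseline factors will be made using the Cox proportional hazards model".

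**The concern.** A covariate earns its place in a Cox model by predicting the outcome. The 7.2.1 rule asks a different question: whether the arms happen to differ on that covariate. When allocation is random and concealed, the answer carries no information about prognosis. A strong predictor that is well balanced stays out, and an irrelevant factor with a chance imbalance goes in.

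Two things are at stake. First, leaving out prognostic factors in a Cox model pulls the treatment hazard ratio toward 1 and loses power. Secondly, nobody can say which model will be fitted until the arms have been compared. The section does not name the test, does not explain what entering a factor separately means, and does not say how selection works with the multiple imputation promised in SAP section 2. Two analysts could follow the text and report different adjusted results.

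**Working it through.** The documents give no operating figure for the 10% rule, so there is none to reproduce.

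**Inputs**
- Threshold 10%, seven candidates: SAP 7.2.1.
- 1:1 allocation, blocks of 10 within centre: SAP 1.5. Nine centres: SAP 1.6.1.
- 1,361 randomised, one not analysed, so 1,360; recruitment August 2007 to June 2011: SAP 1.11.

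**Step 1. Chance of entry.** Under randomisation a valid 10% test rejects with probability 0.10 for each candidate, prognostic or not. Treating the k tests as independent:

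- Seven candidates: expected number entered 7 × 0.10 = 0.7; P(none) = 0.9^7 = 0.478; P(at least one) = 0.522.
- Six candidates: expected number 0.6; P(none) = 0.9^6 = 0.531; P(at least one) = 0.469.

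**Step 2. Why six is the better count.** Blocks of 10 within centre nearly balance calendar time. In a simulation of 1,360 patients in nine centres, with uniform accrual over the recruitment period and a chi-square test of arm by calendar year at 10%, year was never selected in 3,000 runs. This held with equal centre sizes and, in a second set of 3,000 runs, with unequal ones. Uniform accrual and the centre sizes are assumptions.

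**Step 3. What a nil selection means.** If no candidate passes, the first 7.2.1 analysis is the 7.1 model again. This happens in roughly half of trials (48% to 53%). The walk test, which the protocol's description of study tools credits with prognostic value of its own, stays out about 90% of the time. It has no interaction test in 7.2.1 that could bring in its main effect.

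**Step 4. Size of the loss.** The documents give no effect sizes for the candidates, so this step is illustrative. Assumptions: 1,360 patients; seven independent binary candidates with 50% prevalence, three of them prognostic; baseline hazard 0.3 per year; uniform censoring between 1 and 5 years; treatment HR 0.85; about 740 events; 1,500 runs per scenario. Monte Carlo error is about 1.3 points on each power figure. The four fixed covariates were not simulated.

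| HR of each prognostic candidate | Power: no candidates | Power: 10% rule | Power: all seven | All seven minus rule | Mean HR: rule / all seven |
|---|---|---|---|---|---|
| 1.3 | 57.4% | 57.9% | 59.9% | 2.0 points | 0.851 / 0.848 |
| 1.6 | 56.2% | 55.6% | 60.1% | 4.5 points | 0.857 / 0.848 |
| 2.0 | 48.7% | 49.3% | 59.3% | 10.0 points | 0.867 / 0.851 |

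Power under the rule stays within a point of using no candidates at all, so the rule recovers almost none of the available gain. In these runs prognostic and non-prognostic candidates were each selected about 9% to 12% of the time.

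**Step 5. Type I error.** With a true treatment HR of 1, rejection at the two-sided 5% level under the rule was 3.7%, 4.1% and 3.5% for candidate HRs of 1.3, 1.6 and 2.0. It is not inflated.

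**The case against.** The strongest defence is that the rule touches nothing that decides the trial. The primary analysis and all 7.2.2 analyses have fixed lists, the 7.2.1 analyses are labelled secondary, type I error is preserved, and the likely loss is a few power points. All of that stands, and it limits the weight of the point. It does not make the rule useful: an additional adjustment that is empty about half the time is a poor sensitivity analysis.

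A reader might also infer more than the documents support:

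- **That the 10% rule keeps recruitment track out of the primary model.** It does not. Track is absent from 7.1 because of that section's own fixed list. In 7.2.1 it is a named candidate, and a standard arm-by-track interaction model would carry its main effect.
- **That track must be added to 7.1 because NYHA class II enters only through the hospital track.** SAP 1.3 does say "III-IV for patients recruited from the community". But the first amendment in the Summary of Changes brought that limit in only on 18 February 2008. Before then, community patients could qualify on other criteria without being class III or IV. The documents give no prognostic strength for track.
- **That the SAP abandoned a fixed protocol list and wrongly dropped creatinine.** The protocol introduces its factors as examples, and a change between protocol and SAP is not in itself a fault.
- **That the standard errors are invalid because they ignore selection.** The simulation shows no excess of false positives.

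One practical objection also stands. Appendix C of the protocol records an untested walk as 000, so forcing the walk test in without recoding would treat those patients as having walked 0 metres.

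**Conclusion.** The point holds for the three Cox analyses in SAP 7.2.1 and no further. Each candidate enters with about 10% probability regardless of prognosis, recruitment year with almost none, and in 48% to 53% of trials nothing is added. These percentages assume independent candidates.

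The harm is modest: an adjustment set not known in advance, lost power, and a hazard ratio pulled slightly toward 1. The loss is about 2 to 4.5 power points if three candidates each have a hazard ratio of 1.3 to 1.6, and 10 points at 2.0. Those sizes rest on the assumed simulation settings, not on trial data. Neither the validity of the primary analysis nor the type I error rate is in question. The change is worth making because a pre-specified set is better and nearly free.

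**What to change.** In SAP 7.2.1, delete the 10% imbalance test. Name in advance a set of covariates chosen on prognostic grounds from the baseline factors already listed (for example 6-minute walk test, recruitment track, aetiology, LVEF type and diabetes), entered beside the four fixed factors whatever their balance. Baseline comparisons can still be tabulated, but should not steer the model.

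Two details need settling at the same time. Recode a walk-test entry of 000 that means not tested as missing, and impute it under section 2. If medication adherence is kept, define its baseline version, because 7.2.2 gives scoring only for the endpoint.

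The cost is SAP wording before analysis, a few degrees of freedom with 1,360 patients, and some imputation, which section 2 promises only as far as possible. Adding recruitment track to the 7.1 model, or creatinine to the 7.2.1 set, is optional; the documents do not require either.
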